Wake Forest University School of Medicine

Effect of epidural saline on duration and spread of subsequent spinal analgesia/anesthesia using a CSE technique

Principal Investigators: [name].: [name]

Funding: Funding is provided by the Department of Obstetrical Anesthesiology

Background:

Combined spinal epidural labor analgesia (CSE) is a common technique to provide rapid relief of labor pain. In parturients requesting labor analgesia who are appropriate for a combined spinal epidural technique (CSE), the spinal drugs are typically 1.75 to 3.0 mg of bupivacaine and 10-20 micrograms of fentanyl administered intrathecally. Combining bupivacaine and fentanyl provides synergistic effect leading to longer duration of analgesic effect. However, the pruritus that frequently occurs after the administration of intrathecal fentanyl can be particularly bothersome to some patients. We are interested in minimizing the bothersome side effects of intrathecal narcotics as well as potentially increasing the level of sensory block and the analgesia duration of the spinal block by injecting a predetermined amount of normal saline into the epidural space via the epidural needle prior to performance of the spinal block without narcotic while using a CSE labor analgesic technique. Injecting normal saline into the epidural space after but not before an intrathecal injection has been termed epidural volume extension (EVE) and has been shown to increase the cephalad spread of the block. The mechanism of extension of spinal anesthesia was suggested to be mainly the result of a volume effect in which the dural sac is compressed by the injectate which results in a cephalad shift of CSF containing local anesthetic.^{1,2} The effect of epidural injectate volume on an existing spinal block has been studied but with inconsistent clinical findings in which the studies were limited by either a small sample size, a small volume of epidural injectate or variable time interval from spinal block administered and being already “fixed”. However, none of the studies have evaluated the clinical effect of a pre-existing epidural volume injection on a subsequently performed spinal block as we propose to study. The study results will be clinically relevant not only for combined spinal epidural labor analgesia but also for those patients requiring an alternative neuraxial block after a failed epidural block with a large volume of epidural drugs administered. Higuchi estimated a 2.0 ± 1.0 ml to

7.2 +/-ml reduction in mean lumbosacral CSF volume lasting for 30+ minutes and alterations in CSF velocity waveform, both associated with a 5 to 15 ml epidural volume injection with an intact dura.³ Our study is designed to better understand the clinical effects and mechanism of pre-existing epidural injectate volume effect on subsequently performed spinal block.

Objective:

To compare in a controlled, randomized prospective fashion the clinical effect and mechanism of pre-existing epidural saline volume effect on subsequently performed spinal block. Our hypothesis is that 15 ml of a pre-existing epidural injectate volume will significantly increase the level of sensory block and increase the analgesic duration of action in a subsequently performed spinal block.

Methods and Measures

Design and Outcome Measures: This study is a prospective randomized double-blind study whereby the patients will be randomized to one of two groups with either 0 ml or 15 ml of epidural saline injections followed by injection of 3 mg of isobaric bupivacaine intrathecally. Primary outcome measures are highest sensory blockade level to pinprick and to cold. We divided anesthesia dermatome levels to a total of 20 levels from sacral (1 level) then L5 to T1 (as 17 levels) and then C7 (1 level) and C6 or higher as another level. Modified Bromage Motor Scale will be used to assess the amount of motor blockade in the lower extremities.

Secondary outcome measures are the following:

- 1.) Time to Onset of analgesia (VAS <=3)
- 2.) Duration of analgesia (time to request additional analgesia)
- 3.) Time to highest sensory blockade level
- 4.) Time for 2 dermatome level regression of sensory block
- 5.) Time for regression of motor blockade
- 6.) Occurrence of common spinal/epidural side effects: hypotension, fetal bradycardia, vasopressor use (ephedrine), excessively high blocks (higher than T4) and postdural puncture headache

Setting: The study will take place on the labor and delivery suite at Forsyth Medical Center.

Protocol and Procedures:

A. 90 healthy women with uncomplicated pregnancies in early labor (≥ 2 cm but ≤ 6 cm cervical dilation) requesting neuraxial analgesia will be consented to participate to obtain 60 evaluable subjects enrolled in this randomized controlled trial. Patients will be greater than 12 years of age, have an assigned ASA physical status 1 or 2 with a singleton pregnancy. Patients with contraindications to neuraxial anesthesia, inappropriate for study, or with allergies to drugs used in the study will be excluded. Patients inappropriate for study would include those with an assigned ASA status 3 or 4, advanced labor (> 6 cm cervical dilation) or less than 12 years of age. Patients with the potential for distorted epidural anatomy, such as Harrington rods or prior back surgery, will also be excluded.

B. Patients will be randomized into 1 of 2 groups:

Group 1. 45 subjects Epidural space will be identified with loss of resistance to minimal air or saline ($<0.2-0.3$ ml) with a 17 gauge epidural needle. Then, after 20-30 seconds, the spinal needle will be inserted via the epidural needle in the usual manner and 3 mg isobaric bupivacaine (1.2 ml of 0.25% isobaric bupivacaine) will be given intrathecally.

Group 2. 45 subjects Epidural space will be identified with loss of resistance to minimal air or saline ($<0.2-0.3$ ml) with a 17 gauge epidural needle. Normal saline 15 ml will then be administered through the epidural needle over approximately 20 seconds and held for another 10 seconds. The spinal needle will then be inserted via the epidural needle in the usual manner and 3 mg isobaric bupivacaine (1.2 ml of 0.25% isobaric bupivacaine) will be given intrathecally.

In both groups after administration of intrathecal study drug, the spinal needle will be removed followed by insertion of the epidural catheter as in the usual manner. After placement of the epidural catheter, patients will be returned to the supine position with slight left tilt. Patients will be placed with their head up at an angle of approximately fifteen degrees after the spinal injection. The epidural catheter will not be tested or dosed until the patient requests further analgesia. When additional analgesia is requested, the epidural catheter will be tested and dosed in the customary fashion. The catheter will then be connected to a patient controlled epidural analgesic pump with the settings as per our normal standard of care.

C. All patients will be required to sign an informed consent document prior to participating in the study.

We anticipate that it will take 24 months to enroll and study 60 evaluable patients. The specifics of the research will be explained to patients and any questions will be answered. Patient confidentiality will be maintained.

D. All patients will have a functioning intravenous catheter and receive appropriate intravenous fluid of balanced salt solution prior to insertion of their epidural catheter. The epidural space will be located by the usual technique with the patient in the sitting position using a 17G epidural Tuohy sited at L₃₋₄ +/- 1 intervertebral space. All patients will then have an 18G epidural catheter inserted the customary length (5 cm) into the epidural space. The epidural needle will be removed and the catheter secured.

E. Background information on age, height, weight, gestation age, gravid status, cervical dilation, pitocin usage, and stadol usage will be obtained from patient report or the medical record. Study participants will indicate their level of discomfort at peak contraction on a standard 0-10 verbal analog scale (VAS). We will monitor and record the dermatome, pain score, vital signs, ephedrine usage, maternal vital signs, and fetal heart rate every 5 minutes for 20 minutes after initial spinal drug administration or every 5 minutes for 15 minutes after each subsequent physician epidural drug administration. Patient will also be assessed every 15 minutes until the patient requests additional analgesia. Changes in sensory levels to temperature and pin prick perception will also be assessed using alcohol pads and dull pins, respectively, at these same time intervals. Patients will be monitored in the usual clinical manner. Side effects such as hypotension, fetal bradycardia and post dural puncture headache will be recorded and treated as in our usual clinical practice. Participants will have their need for additional medication be evaluated in the routine fashion, and the amount and type of drug administered will be recorded.

Statistical and Analytical Plan:

SigmaStat for Windows by SPSS Inc is being used for statistical analysis. Based on previous observations and our obstetric anesthesia unit quality assurance data, we estimated one standard deviation of our primary outcome measure (highest sensory dermatome level of block) to be 3 dermatome levels. We considered a clinically significant difference in highest sensory block dermatome level between groups to be 3 dermatome levels. With these assumptions and to detect at least a 3 dermatome level difference in highest sensory block between groups with a power of 0.8 to 0.9 and an alpha of 0.05, the minimum sample size

needed is 30 patients per group. For the secondary outcome measure (analgesic duration of action), we consider a difference of 15 minutes between groups to be clinically significant with an estimated 60 minutes for mean duration of action and a standard deviation of 15 minutes. Similarly, the minimal sample size required to detect a difference of 15 minutes or more in analgesic duration between groups is 23 per group with a power of 0.8 to 0.9 and alpha of 0.05. Furthermore, based on our clinical quality assurance report, labor CSE and epidural analgesia may have up to 30% needing additional supplemental dosing and/or technical technique adjustments to achieve complete labor analgesia. Therefore, we will plan to enroll 45 patients per group to obtain at least 30 evaluable patients per group. The primary outcome in dermatome level difference will be analyzed by ANOVA on ranks using Kruskel Wallis test followed by posthoc Tukey test as appropriate.

Risks:

All the usual risks of epidural catheter placement exist including dural puncture by the epidural needle, threading the epidural catheter into a blood vessel (7-16% risk) or spinal space, the epidural not functioning properly (20-32%), as well as other very rare risks of nerve injury, hematoma, infection and seizures. More common usual risks of headache (approximately 1%) are not increased by the study procedure over the usual combined spinal epidural or epidural technique. Patients will be questioned the day following delivery for the presence of headache as per usual routine postoperative follow up visit. Diagnosis and treatment of a spinal headache will be managed as per our standard of practice. This management includes conservative therapy of pain medication, hydration and caffeine, followed by an epidural blood patch if necessary. A literature search yielded no significant reports of serious adverse events associated with epidural injection of saline. Patients may occasionally experience a sensation of pressure during the saline injection that may be perceived as uncomfortable transiently. Performance of a spinal block after administration of a large amount of epidural injectate can clinically translate to a higher sensory and motor level of spinal block and increase in duration of action, both of which are what this study aims to demonstrate. Researchers have hypothesized that compression of the dural sac by residual anesthetic in the epidural space may result in rostral displacement of the CSF, and with it, the injected spinal drug.^{1,4} Others have estimated that the incidence of high spinal anesthesia when performed after epidural anesthesia is as high as 11% with a mean bupivacaine dose of 12 mg⁵. In this study clinically significant high spinal

blockade is considered to be unlikely and no more than usual epidural or combined spinal epidural analgesia, as we will be using very small doses of bupivacaine and the epidural predistension will be performed using normal saline rather than local anesthetic. A higher number of blocked dermatomes may potentially lead to a greater drop in mean arterial blood pressure compared to the usual epidural. However, this decrease is unlikely to be clinically significant based on a prior study showing only a 6 mmHg difference between 2 mL and 10 mL groups.⁶ Blood pressures will be monitored every minute for 15 minutes after epidural placement and treated as appropriate with intravenous medications and fluid.

Benefits:

A 15 ml pre-existing volume injectate may significantly increase the level of sensory block and increase the analgesic duration of action of a subsequently performed spinal block. Spinal bupivacaine alone for combined spinal epidural analgesia with prior epidural volume injection may also provide the following advantages over traditional CSE with bupivacaine and fentanyl:

Less pruritus or most likely no pruritis (without spinal narcotic)

Potentially provides a form a spinal analgesia with longer duration of action without the need of higher dose of drugs.

Minimizes the time of retrieving and record keeping of narcotic use

Potentially better overall patient satisfaction (with less irritating side effects)

Human Subjects Protection

Informed Consent:

Written informed consent will be obtained from each subject. Study team members or the research nurse will obtain informed consent after patient is admitted for labor and is determined to meet the eligibility criteria for participation. The study and informed consent will be reviewed with the patients, and if applicable their legally authorized representative, in their labor and delivery room. Once signed, a copy of the informed consent form will be placed in the patient's medical record and a copy will be given to the patient for their records.

Confidentiality and Privacy:

Confidentiality will be protected by collecting only information needed to assess study outcomes, minimizing to the fullest extent possible the collection of any information that could directly identify subjects, and maintaining all study information in a secure manner. The master study enrollment log containing the names, group allocation, and date of study will be kept secure in the department of OB Anesthesia, with access limited to designated study personnel. Following data collection subject identifying information will be destroyed at the earliest opportunity, consistent with data validation and study design, producing an anonymous analytical data set. Data access will be limited to study staff. Data and records will be kept locked and secured, with any computer data password protected. No reference to any individual participant will appear in reports, presentations, or publications that may arise from the study.

Data and Safety Monitoring:

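### No sensory reading is required at the request for more analgesia, so a 2-dermatome regression in the last minutes of the spinal block (up to 15) goes unseen

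*Combined protocol and SAP*

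**What the plan says.** Protocol and Procedures, section E, sets three series of readings:

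- "every 5 minutes for 20 minutes after initial spinal drug administration";
- "Patient will also be assessed every 15 minutes until the patient requests additional analgesia";
- "every 5 minutes for 15 minutes after each subsequent physician epidural drug administration".

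Sensory testing is tied to this timetable: "sensory levels to temperature and pin prick perception will also be assessed using alcohol pads and dull pins, respectively, at these same time intervals". Section E does not say whether the 15-minute series is counted from the spinal injection or from minute 20.

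Section B describes the step at the request: "When additional analgesia is requested, the epidural catheter will be tested and dosed in the customary fashion". It names no reading between the request and the dose. The nearest other text, at the end of section E, is "Participants will have their need for additional medication be evaluated in the routine fashion", which mentions no block level or pain score.

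The outcome that depends on this timetable is secondary outcome 4 in Methods and Measures: "Time for 2 dermatome level regression of sensory block". Secondary outcome 2, duration of analgesia, is defined by the request itself.

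**The concern.** Regression by two dermatomes is known only through repeated sensory readings. Once epidural drug is given, a reading no longer describes the spinal block alone, so the request closes the window for outcome 4. The schedule requires no look at the block as that window closes. The last one may have been taken a moment earlier or nearly 15 minutes earlier.

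A woman whose block recedes two levels inside that stretch has regressed before any epidural drug, but no required reading shows it. The documents do not say how she would be recorded. No analysis method can restore a reading that was never taken, so the remedy has to be in the visit schedule.

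**Working it through.** **Inputs from the documents.** Readings at 5, 10, 15 and 20 minutes, then every 15 minutes to the request (section E). Time to request has mean 60 minutes and SD 15, and a 15-minute difference counts as clinically significant (Statistical and Analytical Plan). A mean of 75 (60 + 15) was also run to represent a prolonged arm.

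**The plan's own figure.** These inputs give a standardised difference of 15/15 = 1. With two-sided alpha 0.05, n per group = 2(1.960 + 1.282)² = 21.0, so 22 by the normal formula. The t-test version gives 22.02, so 23. The plan's 23 per group is reproduced at power 0.9.

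**Age of the last reading at the request.** If the request falls at an arbitrary point in a 15-minute interval, the gap G is roughly uniform on 0 to 15 minutes:

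- mean = 15/2 = 7.5 minutes;
- P(G > 5) = 10/15 = 67%;
- P(G > 10) = 5/15 = 33%.

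Simulating normal request times (SD 15) on the actual grid, run as 35, 50, 65… or as 30, 45, 60…, gives a mean gap of 7.4 to 7.5 minutes. The gap exceeds 5 minutes in 66% to 67% of women and 10 minutes in 32% to 33%. Neither the anchoring of the grid nor the mean (60 or 75) matters much. The mean gap is 7.5/60 = 12.5% of the planned mean duration. None of this needs an assumption about regression.

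**Share of regressions missed.** This does need one. Let D be the time by which regression precedes the request, taken as normal with a given mean lag and SD. Assume that a regressed block stays regressed. A regression before the request is missed when it falls after the last reading:

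missed share = P(0 ≤ D < G) / P(D ≥ 0).

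Example with lag 10 and SD 10:

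- P(D ≥ 0) = Φ(1) = 0.841.
- Averaging Φ((G − 10)/10) over G from 0 to 15 gives 0.410, and 0.410 − Φ(−1) = 0.410 − 0.159 = 0.251.
- Missed share = 0.251/0.841 = 0.30.

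Simulated results (request mean 60 or 75, both grids; the four settings agree to within about one percentage point):

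| Mean lag before request (assumed) | SD (assumed) | Regress before request | Seen only with a reading at the request, share of all women | Missed, share of pre-request regressions |
|---|---|---|---|---|
| 30 min | 5 | 100% | 0% | 0% |
| 30 min | 10 | 100% | 2% | 2% |
| 20 min | 5 | 100% | 3% | 3% |
| 20 min | 10 | 98% | 10% | 10% |
| 15 min | 5 | 100% | 13% | 13% |
| 15 min | 10 | 93% | 18% | 19% |
| 10 min | 5 | 98% | 33% | 34% |
| 10 min | 10 | 84% | 25% | 30% |
| 5 min | 5 | 84% | 48% | 57% |
| 5 min | 10 | 69% | 28% | 41% |
| 0 min | 5 | 50% | 37% | 73% |
| 0 min | 10 | 50% | 25% | 50% |

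The last two columns differ because some women have not regressed by the request at all.

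**The case against.** **Regression may come well before the request.** It is counted from the highest level, so two dermatomes can be lost long before pain returns. At an average lag of 30 minutes the schedule misses 2% or less. This stands. A reader might infer that regression is most likely in the unobserved stretch, or settle on one percentage. The documents give no regression times and do not link regression to the request, so only the range can be stated.

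**Duration of analgesia is not damaged.** A reader might infer that time to request is compromised because no pain score or block level accompanies it. It is not: the request is an event recorded in its own right, whatever the reading grid. Separating requests made with a worn-off block from those made with a good one would be an extra, explanatory analysis that the plan does not promise.

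**Motor regression (outcome 5) is a different matter.** Section E names no timetable for the Modified Bromage score at any point, so its difficulty is not specific to the request. One score there would not yield a time to motor regression.

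**The consequence is limited.** The same schedule applies to both groups, and no distortion of the group comparison has been shown. The unobserved stretch cannot exceed 15 minutes, and outcome 4 has no sample-size calculation of its own. All of this stands.

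**A closing look may happen anyway.** The wording of the 15-minute series does not exclude an assessment at the request, and routine evaluation may include one. But nothing requires the sensory level to be tested and recorded before the dose. This point lowers the practical risk without closing the gap.

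**Conclusion.** The point holds for secondary outcome 4 only. The last required spinal-only sensory reading precedes the request by about 7.5 minutes on average and by up to 15. That rests on the schedule and the plan's own mean and SD. The proportion of pre-request regressions lost runs from about 0% to about 73% over assumed mean lags of 30 to 0 minutes and SDs of 5 to 10, and nothing in the documents narrows it.

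The primary outcome is little affected: a gap at the end could hide the highest level only if the block were still rising at the request. This is a low-cost improvement to data collection, not a fault that threatens the trial's main conclusion.

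**What to change.** Add to Protocol and Procedures, section E: at the request for additional analgesia, and before any epidural drug takes effect, record clock time, pinprick level, cold level and pain score at peak contraction. The Modified Bromage score may be added as a descriptive item. Take the readings while the epidural drug is being prepared, so that treatment is not delayed.

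Add to the Statistical and Analytical Plan, for outcome 4:

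- the reading at the request is the last spinal-only reading;
- a regression first seen there is treated as occurring between the previous reading and the request, because the reading shows status by that time and not the exact moment;
- a woman not regressed by then is censored at the request.

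The reading does not remove the need for the censoring rule, so both changes are needed. The cost is one row on the data sheet and a minute or two of examination while the patient is in pain.

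### The minimum of 30 per group for the primary outcome does not follow from the stated inputs, which give 17 to 23, and it is not reconciled with the 23 given for duration

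*Combined protocol and SAP*

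**What the plan says.** All the sample size statements are in the Statistical and Analytical Plan.

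- Primary outcome, variability: "we estimated one standard deviation of our primary outcome measure (highest sensory dermatome level of block) to be 3 dermatome levels".
- Primary outcome, difference sought: "We considered a clinically significant difference in highest sensory block dermatome level between groups to be 3 dermatome levels".
- Result: "with a power of 0.8 to 0.9 and an alpha of 0.05, the minimum sample size" then "needed is 30 patients per group".
- Analgesic duration: a 15-minute difference, "with an estimated 60 minutes for mean duration of action and a standard deviation of 15 minutes". The number required "is 23 per group with a power of 0.8 to 0.9 and alpha of 0.05".
- Enrolment, after citing up to 30% of patients who need supplementary dosing or technical adjustment: "we will plan to enroll 45 patients per group to obtain at least 30 evaluable patients per group".
- Primary test: "The primary outcome in dermatome level difference will be analyzed by ANOVA on ranks using Kruskel Wallis test".

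Design and Outcome Measures describes two randomised groups and two primary measures, the highest block to pinprick and to cold. Protocol and Procedures, items A and B, give 45 per group, 90 in all, to obtain 60 evaluable. The documents state neither the sidedness of alpha nor any division of alpha between the two primary measures.

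**The concern.** The paragraph performs what is in effect one calculation twice and reports two answers. The primary outcome has a standardised effect of 3/3 = 1.0 and duration has 15/15 = 1.0. Alpha and the power range are the same, and the second calculation is introduced as similar to the first. Yet the results are 30 and 23.

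The total enrolment is built on the 30. If that figure is not what the inputs give, a reader cannot tell whether it is a deliberate margin, an allowance left unwritten, or a calculation carried over from a different design. The stated power range would then also misdescribe the trial.

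**Working it through.** **Inputs** (Statistical and Analytical Plan, unless noted): difference 3 levels, SD 3 levels, so d = 3/3 = 1.0; alpha 0.05, taken as two-sided because sidedness is not stated; power 0.80 and 0.90; two equal groups (Protocol and Procedures, item B).

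**1. Normal approximation.** n per group = 2(z for alpha/2 + z for power)² / d².

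- 80%: 2 × (1.960 + 0.842)² = 15.7, rounded up to 16.
- 90%: 2 × (1.960 + 1.282)² = 21.01, rounded up to 22.

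**2. Exact two-sample t-test** (noncentral t, 2n − 2 degrees of freedom, noncentrality d√(n/2)).

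- 80%: n = 16.71, so 17 (power 0.807).
- 90%: n = 22.02, so 23 (power 0.912).
- At n = 30 the noncentrality is √15 = 3.87 and the power is 0.968.

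The plan's 23 for duration is therefore reproduced exactly, as the 90% answer. The 30 for the primary outcome is not reproduced.

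**3. Planned rank test.** With two groups the Kruskal-Wallis test is equivalent to a Wilcoxon rank-sum test. Its efficiency relative to the t-test is 0.955 for normal data.

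- 80%: 16.71/0.955 = 17.50, so 18.
- 90%: 22.02/0.955 = 23.06, so 24.
- Power at 30 is about 0.961.

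A simulation agrees. It used 20,000 runs per setting, the tie-corrected Kruskal-Wallis test, and normal data rounded to the 20-level scale, with group centres of 10 and 13 assumed. Power was 0.807 at 18, 0.898 at 23, 0.910 at 24 and 0.960 at 30.

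**4. Could another reading give 30?** All rows use d = 1.0.

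| Variant | n at 80% | n at 90% |
|---|---|---|
| One-sided 0.05, t-test | 14 | 18 |
| Two-sided 0.05, worst-case rank efficiency 0.864 | 20 | 26 |
| Alpha 0.025 per primary measure, efficiency 0.955 | 22 | 28 |
| Alpha 0.025 per primary measure, efficiency 0.864 | 24 | 31 |
| Alpha 0.01, t-test | 26 | 32 |
| Three-group ANOVA, alpha 0.05 | 21 | 27 |
| Four-group ANOVA, alpha 0.05 | 23 | 30 |

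The rank-test rows divide the unrounded t-test n by the efficiency; rounding first can add one patient. The ANOVA rows assume a maximum difference of 1 SD with the other means at the midpoint. A two-group t-test also needs 30 at 90% power if the SD is about 3.5 (3.52) instead of 3. Every route to about 30 needs an input that the plan does not state.

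**5. Non-evaluable allowance.** It does not explain the 30, because the plan applies it afterwards: 30/(1 − 0.30) = 42.9, so 43, and the planned 45 covers that.

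**6. What 30 per group protects against.** Power for a 3-level difference at 30 per group:

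| SD (levels) | t-test | Rank test |
|---|---|---|
| 3 | 0.968 | 0.961 |
| 3.5 | 0.904 | 0.890 |
| 4 | 0.815 | 0.797 |

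**The case against.** The best defence is that 30 may contain a legitimate allowance. The trial has two primary measures and a rank test. Splitting alpha to 0.025 and using the worst-case rank efficiency gives 24 to 31 per group, with power 0.897 at 30, inside the stated range. With the usual efficiency the same split gives 28 (29 if the t-test figure is rounded up first), only one or two short. In addition, no test is named for duration, so equal standardised effects need not give exactly equal sample sizes. Extra patients also do not harm the inference.

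Part of this stands. The documents do not show that a wrong calculation was made; they show that 30 cannot be traced to the inputs given. It is also true that nothing in the analysis or error control changes.

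The rest does not remove the point. The plan states alpha 0.05, with no split and no efficiency factor, and presents 30 as the minimum that follows from its listed assumptions. Using a rank test for one outcome and a t-test for the other accounts for about one patient per group, not seven. If 30 was a margin or an allowance, the plan needs to say so.

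**Conclusion.** The concern holds, at low severity. On the stated inputs the requirement is 17 to 23 per group by t-test, or about 18 to 24 by the planned rank test. The stated 30 is 6 to 7 per group above the 90% figure (30 − 24 and 30 − 23), and its power is about 0.96 to 0.97, not 0.8 to 0.9. The 23 for duration is correct at 90% power and contradicts the 30 unless some unstated input separates them.

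The discrepancy is conservative. It costs no power and leaves type I error unchanged, and it gives real protection if the SD has been underestimated. The conclusion assumes two-sided alpha and roughly normal dermatome levels. One-sided testing would widen the gap, and the worst-case rank efficiency alone (20 to 26) would not close it.

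**What to change.** Leave the 30 evaluable and 45 enrolled per group as they are, and reword the sample size paragraph:

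- Replace the claim that 30 is the minimum for 80 to 90% power with a statement of what it delivers: 30 evaluable patients per group give about 96% power (two-sided rank test, alpha 0.05) for a 3-level difference if the SD is 3.
- Give the source of the 30. If an allowance was used (an alpha split, an efficiency factor, a larger SD), enter it with its value. If 30 was chosen as a margin against a larger SD, say so and give the power it retains: about 0.89 to 0.90 at SD 3.5 and about 0.80 at SD 4. The authors should use whichever explanation is true.
- Reconcile it with duration, for example: 23 per group give about 91% power for a 15-minute difference with SD 15, and the 30 evaluable per group give about 97%. Both figures assume a two-sided t-test at alpha 0.05. The plan names no test for duration, so the authors should confirm it.

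The cost is rewording one paragraph. Recruitment targets do not change.
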